### 3.5 SAMPLE SIZE CONSIDERATIONS

A total of 12 subjects will be randomized to the study, with 6 subjects per treatment schedule arm.

Subject numbers are based on the following guidance: In study ACH-CYT-01, geometric mean  $AUC_{0-\infty}$  values in the fed and fasted states were 168 ng.h/mL and 173 ng.h/mL respectively (yielding a geometric mean ratio of 0.97) with an intra subject CV% of approximately 6%. Geometric mean  $C_{max}$  values in the fed and fasted states were 22.3 ng/mL and 29.8 ng/mL respectively (yielding a geometric mean ratio of 0.75) with an intra subject CV% of approximately 23%. Although this study is not a formal comparison of bioequivalence the assumptions used for a typical bioequivalence study have been used in order to estimate an appropriate sample size. Based on the assumption that similar results will be observed for this study, a sample size of 4 subjects would be sufficient to detect a 20% difference in  $AUC_{0-\infty}$  between the treatments with a power of 80%, an alpha of 5% and a fed/fasted ratio of 1. Therefore, 12 subjects, which is the minimum number of subjects recommended for this type of trial, should be sufficient to compare the bioavailability with respect to AUC in the fed and fasted states. Given that the  $C_{max}$  geometric mean ratio observed in the previous study did not fall within the bioequivalence range, likely due to the slower rate of absorption in the fed state, the sample size has been based on  $AUC_{0-\infty}$ .

Subjects who withdraw from the study before receiving any study medication will be replaced. Subjects who are withdrawn from the study due to significant drug-related AEs will not be replaced. Replacement of all other subjects withdrawn from the study after receiving study medication will be decided on a case-by-case basis by the Principle Investigator (or delegate) and Sponsor.

### 3.6 RANDOMISATION

Subjects will be allocated to a treatment schedule (sequence) in accordance with a randomisation code produced by [REDACTED] using the PROC PLAN procedure of SAS® version 9.3. Treatment schedules are as follows:

#### **Schedule A (6 subjects):**

- Period 1: Cytisine (2 x 1.5 mg tablets) will be administered 30 minutes after the start of a high fat breakfast (fed state) with 240 mL water.
- Period 2: Cytisine (2 x 1.5 mg tablets) will be administered after the overnight fast of at least 10 hours (fasting state with 240 mL water).

#### **Schedule B (6 subjects):**

- Period 1: Cytisine (2 x 1.5 mg tablets) will be administered after the overnight fast of at least 10 hours (fasting state with 240 mL water).
- Period 2: Cytisine (2 x 1.5 mg tablets) will be administered 30 minutes after the start of a high fat breakfast (fed state) with 240 mL water.

Subjects will be numbered sequentially from 001 (i.e. 001, 002 etc.). Any replacement subjects will be assigned the same randomisation as the subjects they are replacing with 100 added to the subject number (i.e. 101 would replace 001 etc.).

## 4 STUDY VARIABLES AND COVARIATES

### 4.1 PRIMARY VARIABLES

The primary plasma cytosine pharmacokinetic endpoints for this study are as follows:

- $C_{max}$  Maximum observed plasma concentration post dose, obtained from the observed concentration versus time profile.
- $AUC_{0-\infty}$  Total area under the plasma concentration-time curve (AUC) from zero to infinity, calculated as  $AUC_{0-\infty} = AUC_{0-t} + (C_{last}/\lambda_z)$ , where  $C_{last}$  is the last measurable plasma concentration and  $\lambda_z$  the apparent terminal elimination rate constant.

The primary urine cytosine pharmacokinetic endpoints for this study are as follows:

- $A_e$  Amount excreted in urine over time.
- $A_e\%$  Percentage of drug excreted in urine.

### 4.2 SECONDARY VARIABLES

The secondary plasma cytosine pharmacokinetic endpoints for this study are as follows:

- $T_{max}$  Time of occurrence of maximum observed plasma concentration.
- $AUC_{0-t}$  AUC from the time of zero to the last sampling time at which concentrations were at or above the lower limit of quantification (LLOQ), calculated by the linear-up/log-down trapezoidal rule.
- %AUC Residual area or percentage of extrapolated part for the calculation of  $AUC_{0-\infty}$ , calculated as  $100*[1-(AUC_{0-t}/AUC_{0-\infty})]$ .
- $\lambda_z$  Apparent terminal elimination rate constant.
- $t_{1/2}$  Apparent terminal elimination half-life, calculated from  $\ln 2/\lambda_z$ .
- $CL/F$  Apparent total body clearance.
- $Vd/F$  Apparent volume of distribution.

The safety endpoints for this study are as follows:

- Adverse events (AEs).
- Laboratory safety data (biochemistry, haematology, urinalysis and microscopy).
- Vital signs (supine systolic/diastolic blood pressure, pulse rate and oral temperature).
- 12-lead ECG (heart rate, PR interval, QRS width, QT interval and QT interval corrected using Fridericia's formula (QTcF interval)).

## 5 DEFINITIONS AND DERIVED VARIABLES

**Study drug/IMP:** Study drug/IMP means 3 mg cytosine (2 x 1.5 mg cytosine tablets).

**Treatment:** Treatment means 3 mg cytosine in the fed or fasted state.

**Baseline:** In general, baseline is defined by subject and by variable as the last non-missing value (including repeats) before the first dose of study drug. This is normally the pre-dose assessment on Day 1 but if this assessment is missing (or not planned) then the assessment at the Screening/Day 0 visit will be used instead if available.

**Study Day:** Study day is the number of days since start of treatment where the date of first dose is counted as Day 1.

**Bleed Time Deviation:** Actual time of blood sample – theoretical time of blood sample.

**Protocol Deviation:** a deviation related to study inclusion or exclusion criteria, conduct of the trial, subject management or subject assessment. This refers to any change, divergence, or departure from the study design or procedures defined in the protocol. Deviations recorded by the Project Manager or detected by Data Management or by statistical programming checks will be identified and discussed at the Data Review Meeting (DRM) before Database Lock (DBL). All protocol deviations within the study database will be classified as either 'Major' or 'Minor' prior to DBL, details of which will be included within the Protocol Deviations listing.

## 6 ANALYSIS SETS

Membership of the analysis sets will be reviewed and agreed prior to DBL. These will be reviewed by the Sponsor, Study Statistician, PK analyst and Project Manager and signed off. If PK data is not available at the time of DBL, then subjects will be assumed to be included in the analysis set unless the PK data provide reason to exclude a subject, in which case this will be discussed with the Sponsor and documented within the Analysis Sets listing (Listing 16.2.3.1).

### 6.1 SAFETY SET

All randomised subjects who receive at least one dose of cytosine will constitute the Safety Set.

This analysis set will be used for baseline and safety summaries as well as for all study listings.

### 6.2 PK SET

The PK Set will include all subjects who receive both doses of cytosine and have sufficient plasma concentration-time profiles complying with the following criteria:

- Do not have an occurrence of vomiting or diarrhoea which renders the concentration profile unreliable (e.g. if vomiting occurs at or before 2 times median  $T_{max}$ );
- Do not use a concomitant medication which renders the concentration profile unreliable;
- Do not have a pre-dose concentration that is greater than 5% of the corresponding  $C_{max}$ ;

- Have at least one evaluable concentration that is preceded by a lower evaluable concentration and followed by a lower evaluable concentration for the calculation of  $C_{max}$ ,  $T_{max}$  and AUCs (i.e. at least 3 evaluable concentrations in total);
- Do not violate the protocol (major protocol deviation) in a way that may invalidate or bias the results.

### 6.3 URINE EXCRETION SET

The Urine Excretion Set will include all subjects who receive both doses of cytosine and have sufficient urine excretion profiles complying with the following criteria:

- Do not have any missing urine excretion collections (i.e. missing urine in a collection period specified in section I.4.3) which renders analysis of overall excretion unreliable;
- Do not have an occurrence of vomiting or diarrhoea which renders the urine excretion profile unreliable (e.g. if vomiting occurs at or before 2 times median  $T_{max}$  derived from plasma data);
- Do not use a concomitant medication which renders the concentration profile unreliable;
- Do not violate the protocol (major protocol deviation) in a way that may invalidate or bias the results.

## 7 SAFETY MONITORING

No interim safety analyses are planned for this study.

## 8 INTERIM ANALYSES

No interim efficacy/PK analyses are planned for this study.

## 9 DATA

### 9.1 CRF DATA

CRF data will be provided by [REDACTED] Data Management to the Statistics department as SAS datasets in [REDACTED] standard format. SDTM datasets will be derived from the raw database and ADaM from SDTM. Both SDTM and ADaM domains will be used for programming the outputs to be included in the Clinical Study Report (CSR). SDTM/ADaM programming will begin when populated [REDACTED] standard SAS datasets are available.

#### 9.1.1 Laboratory Data

Transfers of safety laboratory data will be available from the Pathology laboratory and delivered to Data Management via electronic transfer and stored within the study database. Details of laboratory data are documented in the Data Management Plan (DMP). Populated test transfers will be received before programming can start. The following results will be included:

- **Haematology:** Haemoglobin, haematocrit, mean cell volume, mean cell haemoglobin, mean cell haemoglobin concentration, red blood cells, white blood cells, neutrophils, lymphocytes, monocytes, eosinophils, basophils and platelets.
- **Biochemistry:** Total protein, albumin, total bilirubin, alanine transaminase, aspartate transaminase, gamma glutamyl transferase, alkaline phosphatase, glucose, sodium, potassium, calcium, bicarbonate, creatinine and urea.
- **Urinalysis:** Glucose, specific gravity, protein, leucocytes, ketones, urobilinogen, bilirubin, nitrites, pH and blood.
- **Microscopy:** In the event that the 'dipstick' is positive, RBCs, WBCs, epithelial cells, crystals, bacteria and casts will be examined microscopically.
- **Virology:** Hep B, Hep C and HIV.
- **Drugs of Abuse and Alcohol:** Urine alcohol and drugs of abuse screen: cannabinoids, amphetamines, cocaine, benzodiazepines, opiates and cotinine.
- **Pregnancy/post-menopausal assessment:** serum/urine pregnancy test and follicle stimulating hormone.
- **Other parameters:** Any further parameters that are taken that are not included as part of the above categories will be included in an 'Other Laboratory Data' listing.

### 9.1.2 Pharmacokinetic Data

Plasma and urine concentration data will be received as an Excel file from the Bioanalytical department via an electronic transfer and stored as a SAS dataset. This data will then be stored in the appropriate SDTM domain and subsequent ADaM domain which will be used to produce the file provided to the pharmacokinetic team in order to derive the PK parameters using Phoenix WinNonlin 6.4. Derived PK parameters will be received by the Statistics department from the Project Manager/PK analyst in a SAS.xpt file in an agreed format and then stored as a SAS dataset and subsequently within SDTM/ADaM domains.

## 9.2 RANDOMISATION LIST

The randomisation list will be uploaded to a SAS dataset and incorporated into the relevant SDTM/ADaM domains.

## 9.3 PROGRAMMING AND DATA REVIEW

Programming of datasets, tables, figures and listings may be ongoing while study data management activities are in progress.

Prior to DBL, a review of the clinical database (i.e. CRF data, laboratory data) in the form of Excel data listings will be conducted. A Data Review Meeting (DRM) will be held to discuss the outcome of this review, any potential impact on the analyses, analysis sets and protocol deviations. Once all data issues have been resolved and the analysis sets approved, the database will be locked. The SDTM/ADaM datasets will be finalised and the final run of outputs and quality control (QC) will take place.

## 10 STATISTICAL METHODS

### 10.1 GENERAL PRINCIPLES

- All statistical methods will be based on the International Conference on Harmonisation (ICH) E9 document “Statistical Principles for Clinical Trials”.
- All data collected will be presented within data listings and any unscheduled visits will be listed.
- Data will be summarised by treatment and overall (data from both treatments pooled) where appropriate. The format of the summaries is defined in the shells at the end of this document.
- In summary and analysis tables of continuous variables, standard descriptive statistics (N [number within population], n [number of observations included in analysis], mean, standard deviation [SD], median, minimum and maximum) will be presented. Least squares mean (LS mean) and 90/95% confidence interval (CI) will be presented in the statistical analysis outputs as appropriate. For PK summaries, geometric mean, and coefficient of variation (%CV) will also be used to summarise the data.
- Unless otherwise specified, the minimum and maximum statistics will be presented in summary tables to the same number of decimal places as the original data. The mean, median, LS mean, geometric mean and CI will be presented to one more decimal place than the original data. SD will be presented to two more decimal places than the original data. %CV will be presented to one decimal place.
- In summary tables of categorical variables, the number of non-missing observations by category will be presented along with percentages. Unless otherwise specified, the denominator for each percentage will be the number of non-missing observations. All percentages will be presented to one decimal place.
- All plots will use a linear time scale for the nominal times of the visits and will be labelled by time point.
- Original values will be used in summary tables, unscheduled measurements will be listed only. However, where repeats of baseline values occur, the last assessment will be used within any summary tables and used to calculate change from baseline. In case an unscheduled measurement is performed immediately after the scheduled measurement due to an error in the original measurement, the unscheduled measurement will be included in the analysis and the original erroneous measurement will be excluded.
- The date format for all output presentations will be as captured in the database.
- All statistical analysis will be performed using SAS 9.3 or higher.
- All hypothesis testing will be carried out at the 5% (2-sided) significance level unless stated otherwise.
- P-values will be rounded to four decimal places. P-values less than 0.0001 will be reported as <0.0001 in tables.
- Generally, character values will be left aligned and numeric values will be decimally aligned.
- If any of the assumptions underlying the formal statistical methods proposed are violated during the analysis of the final data, alternative statistical methods will be used and any changes documented in the statistical methods section of the clinical study report (CSR), including the rationale for use.

- For numeric data which includes non-numeric values (e.g. PK data reported as BLQ or laboratory results reported as < 10 or >100) the following principles will be applied when summarising the data:
  - BLQ will be replaced with a zero.
  - Results reported as <x or >x will be treated as x.

## 10.2 STRATIFICATION AND COVARIATE ADJUSTMENT

Not applicable.

## 10.3 MISSING DATA

Generally, no methods to impute missing data will be used. However, for the purpose of calculating change from baseline, in the instance of a missing baseline result for Period 1 (generally the assessment at Day 1, Pre-Dose) the results obtained at the Screening/Day 0 visit will be used instead, if available. Missing Period 2 baseline results will not be replaced.

In the instance of missing pharmacokinetic blood samples, the linear trapezoidal rule will be employed between the samples immediately before and after the missing sample for the AUC calculations.

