12.3. Determination of Plasma and Urine Drug Concentrations

Cytisine concentrations (ng/mL) in plasma and urine will be determined using a validated liquid chromatography tandem mass spectrometry method and will be conducted in accordance with Good Laboratory Practice regulations and guidelines. Methods validation must be completed prior to start of the analysis.

The sample analysis will only begin after the last sample of a study subject is collected. All samples from each subject will be analyzed in the same analytical batch. In each run, standard and quality control samples will be distributed throughout the batch containing study samples. Samples with concentrations above the ULOQ will be diluted and re-assayed.

Full details, including the lower (LLOQ) and upper (ULOQ) limits of quantification range, will be provided in a Bioanalytical Phase Plan written by [REDACTED]

Plasma and urine samples of withdrawn subjects should also be analysed for drug concentrations and pharmacokinetic parameters (providing withdrawal was not due to withdrawal of consent).

Unacceptable values due to analytical reasons will be handled in accordance with the Bioanalytical Phase Plan.

Details of the methodologies used and the results obtained, including details of re-measured samples, will be given in the Analytical Study Report (ASR).

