15.6. Estimation of pharmacokinetic parameters

Plasma: The following pharmacokinetic parameters for cytisine will be derived by standard non-compartmental methods from the concentration versus time profiles:

Table 10: Cytisine Pharmacokinetic Parameters

Parameter	Description
C_{\max}	Maximum observed plasma concentration post dose, directly obtained from the observed concentration versus time profile.
T_{\max}	Time of occurrence of maximum observed plasma concentration.
AUC_{0-t}	Area under the plasma concentration versus time curve (AUC) from time zero to the last sampling time at which concentrations were at or above the LLOQ, calculated by the linear-up/log-down trapezoidal rule.
$AUC_{0-\infty}$	Total AUC from time zero to infinity, calculated as $AUC_{0-\infty} = AUC_{0-t} + (C_{\text{last}}/\lambda_z)$, where C_{last} is the last measurable plasma concentration and λ_z the apparent terminal elimination rate constant.
%AUC	Residual area or percentage of extrapolated part for the calculation of $AUC_{0-\infty}$, calculated as $100 * [1 - (AUC_{0-t}/AUC_{0-\infty})]$
λ_z	Apparent terminal elimination rate constant.
$T_{1/2}$	Apparent terminal elimination half-life, calculated from $\ln 2/\lambda_z$.

No values of λ_z , $AUC_{0-\infty}$, %AUC and $T_{1/2}$ will be reported for cases where λ_z cannot be reliably determined.

Pharmacokinetic parameters will be estimated from the plasma concentration versus time profiles for all subjects in the safety analysis set. Actual sampling times will be used for the pharmacokinetic analysis. All calculations will be performed using raw data.

The terminal elimination rate constant (λ_z) will be determined by plotting the concentration data versus time on a semi-logarithmic scale. The parameter will be estimated by linear least square regression analysis, using the last three (or more) non-zero concentrations. The upper and the lower timepoints, as well as the number of timepoints, used for λ_z estimation will be reported.

AUC_{0-t} will be calculated by the linear-up/log-down trapezoidal method.

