15.9. Procedures for Deviations from Planned Analyses

The planned statistical analyses for this study will be described in detail in a SAP. Modifications or additions to the analyses described above will be described in the SAP. Any decisions to deviate from the planned analyses described in the protocol and SAP will be documented in the clinical study report. The clinical study report will also provide a detailed explanation for any deviations from the planned analyses.

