#### 11.4.2 Derived Plasma PK Parameters

The following derived pharmacokinetic parameters of cytosine in plasma will be determined using WinNonlin Phoenix 6.4 from the individual concentration versus time profiles using standard non-compartmental methods:

Pharmacokinetic Parameter	Definition	WinNonlin computation	WinNonlin Parameter Name
$C_{max}$ (ng/mL)	Maximum observed plasma concentration post dose	Maximum observed concentration, occurring at $T_{max}$ . If not unique, then the first maximum is used.	Cmax
$T_{max}$ (h)	Time of occurrence of maximum observed plasma concentration	Time of maximum observed concentration. If the maximum observed concentration is not unique, then the first maximum is used.	Tmax
$AUC_{0-t}$ (h*ng/mL)	The area under the plasma concentration-time curve (AUC) from 0 h to the last sampling time at which concentrations were at or above the LLOQ	AUC measured from the concentration at time of dosing to the last measurable positive concentration. The AUC is computed using the linear-up/log-down trapezoidal method.	AUClast
$AUC_{(0-inf)}$ (h*ng/mL)	The AUC from 0 h extrapolated to infinity	AUC measured from the concentration at time of dosing extrapolated to infinity based on the last observed concentration. $= AUC_{0-t} + \frac{C_{lastobs}}{\lambda_z}$	AUCINF_obs
$AUC_{\% \text{ extrapolated}}$ (%)	Residual area.	Percentage of $AUC_{0-inf}$ due to extrapolation from time of last measurable positive concentration to infinity. $= \frac{AUC_{0-inf} - AUC_{0-t}}{AUC_{0-inf}} \cdot 100$	AUC_%Extrap_obs
$\lambda_z$ (1/h)	Apparent terminal elimination rate constant.	First order rate constant associated with the terminal (log-linear)	Lambda_z

		portion of the curve. Estimated by linear regression of time vs. log concentration; the regression analysis should contain data from at least 3 different time points in the terminal phase.	
$t_{1/2}$ (h)	Apparent terminal elimination half-life.	$= \ln(2) / \lambda_z$	HL_Lambda_z
CL/F	Apparent total body clearance.	$= Dose / AUC_{0-inf}$	Cl_F_obs
Vd/F	Apparent volume of distribution based on the terminal phase.	$= \frac{Dose}{K_{el} \cdot AUC_{0-inf}}$	Vz_F_obs

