The terminal elimination rate constant ( $\lambda_z$ ) will be determined by plotting the concentration data versus time on a semi-logarithmic scale. The parameter will be estimated by linear least square regression analysis, using the last three (or more) non-zero concentrations. The upper and the lower time points, as well as the number of time points, used for  $\lambda_z$  estimation will be reported. Values of  $\lambda_z$ ,  $AUC_{0-\infty}$ , %AUC and  $t_{1/2}$  will not be reported for cases where  $\lambda_z$  cannot be reliably determined.

$AUC_{0-t}$  will be calculated using the linear-up/log-down trapezoidal method.

For the calculation of derived pharmacokinetic parameters, concentrations below the limit of quantification (BLQ) will be assigned a value of zero. In case of a deviation from the theoretical time, the actual time of blood sample will be used in the calculation of the derived pharmacokinetic parameters. Should the actual time be unavailable but a blood sample was taken, the nominal time point will be assigned.

Derived pharmacokinetic parameters will be listed and summarised for each treatment. The descriptive statistics presented will be N, n, arithmetic mean, arithmetic standard deviation (SD), coefficient of variation (CV%), minimum, median, maximum and geometric mean (with the exception of  $T_{max}$ ).

If no reliable PK parameter can be determined for more than a third of the subjects, only n, minimum and maximum values will be presented for that parameter and all other descriptive statistics will be omitted.

Plasma PK parameter data listings will be presented using the Safety Set. Plasma PK data summaries will be presented using the PK Set and also the Safety Set if they differ. All PK parameter data included in listings and summaries will be presented to three significant figures with the exception of the CV% which will be presented to one decimal place.

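### SAP 10.3 uses a plain linear trapezoid across a missing PK sample, against the linear-up/log-down rule stated everywhere else, and this slightly inflates AUC on the declining limb

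*SAP*

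**What the plan says.** Two different rules are given for the same calculation.

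- **SAP 10.3 (Missing Data):** where a blood sample is missing, "the linear trapezoidal rule will be employed between the samples immediately before and after the missing sample for the AUC calculations". Rising and falling segments are not distinguished.
- **Protocol 15.6:** AUC0-t "will be calculated by the linear-up/log-down trapezoidal method".
- **SAP 4.2:** AUC0-t is "calculated by the linear-up/log-down trapezoidal rule".
- **SAP 11.4.2, parameter table:** "The AUC is computed using the linear-up/log-down trapezoidal method". The same entry sets the end of AUC0-t: "AUC measured from the concentration at time of dosing to the last measurable positive concentration".
- **SAP 11.4.2, text below the table:** AUC0-t "will be calculated using the linear-up/log-down trapezoidal method".

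None of the linear-up/log-down statements has an exception for missing samples, and 11.4.2 does not point to 10.3. SAP 1.2 lists three changes from the protocol (a vital signs summary, the analysis-set definitions, and the addition of CL/F and Vd/F). The AUC rule is not among them. Protocol 15.9 does allow the SAP to change the analysis: "Modifications or additions to the analyses described above will be described in the SAP".

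**The concern.** AUC0-∞ is AUC0-t plus an extrapolated tail, and SAP 4.1 makes it a primary endpoint. Under SAP 9.1.2 the PK team derives the parameters in WinNonlin. A PK analyst working from 11.4.2 would use the log rule across a falling gap, while someone checking the result against 10.3 would expect the linear rule. The same subject would then have two different AUC values, each traceable to the SAP.

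The error also has a known direction. The two rules agree on the rising limb, but on a falling segment the linear area always exceeds the log area. A late gap in a fed profile therefore pushes the fed/fasted ratio up, and a late gap in a fasted profile pushes it down. CL/F and Vd/F, which have AUC0-∞ in the denominator, are understated to match.

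**Working it through.** The plan gives no figure for the effect of a missing sample, so there is none to reproduce on this point. Its one design calculation does reproduce: with CV 6%, ratio 1 and limits 0.80 to 1.25, two one-sided tests have power 0.42 at n = 3 and 0.89 at n = 4, so 4 subjects is the smallest number reaching 80%. The 6% CV is used in step 4.

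**1. Inputs.** From the protocol's Table 3: AUC0-∞ 173 (fasted) and 168 (fed) ng.h/mL; half-life 4.59 and 4.77 h; Tmax 0.75 and 2.75 h. Sampling times are the 18 in SAP 11.4.1. The assumed model is one-compartment with first-order absorption:

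C(t) = AUC·k·ka/(ka − k) × [exp(−kt) − exp(−ka·t)], with k = ln 2 / T½

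- Fasted: k = 0.1510/h and ka = 5/h, peak at the 0.75 h sample.
- Fed: k = 0.1453/h and ka = 0.75/h, peak at the 2.5 h sample.

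λz is taken from the last three measurable points, and AUC0-t ends at the last measurable point.

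**2. The two rules over a falling gap of length Δ from C1 to C2.**

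- Linear: Δ(C1 + C2)/2
- Log: Δ(C1 − C2)/ln(C1/C2)

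Fasted, 16 h missing, so the gap is 14 to 24 h (C = 3.252 and 0.718 ng/mL):

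- Linear: 10 × (3.252 + 0.718)/2 = 19.85
- Log: 10 × (3.252 − 0.718)/ln(3.252/0.718) = 16.78
- Excess: 3.07, which is 3.07/172.4 = 1.8% of AUC0-∞

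Fasted, 24 h missing and 48 h measurable, so the gap is 16 to 48 h (C = 2.405 and 0.019 ng/mL):

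- Linear: 38.78; log: 15.80
- Excess: 22.98, which is 13.3% of AUC0-∞

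**3. AUC0-∞ with the linear rule across the gap, relative to the full-sample value.**

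| Missing sample | Fasted | Fed |
|---|---|---|
| 6 h | +0.78% | +0.25% |
| 8 h | +1.68% | +1.60% |
| 12 h | +1.24% | +1.36% |
| 14 h | +0.23% | +0.27% |
| 16 h | +1.78% | +2.12% |
| 14 h and 16 h | +3.67% | +4.32% |
| 24 h, 48 h measurable | +13.3% | +16.5% |
| 24 h, 48 h BLQ | 0.00% | +0.01% (same under log-down) |

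Log-down across the same gaps errs by at most 0.34%. Near the fed peak the pattern differs: with 4 h missing, the linear rule gives −0.28% and log-down −0.45%. The overstatement is therefore claimed only from 6 h onward.

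**4. Trial level.** With 6 + 6 subjects, each subject's log difference carries weight 1/12, so one affected profile with relative error e multiplies or divides the ratio by (1 + e)^(1/12).

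| Case | Shift in ratio | 90% CI half-width (simulated) |
|---|---|---|
| One sample, 6 to 16 h (0.2% to 2.1%) | 0.02% to 0.2% | at most × 1.003 |
| 14 h and 16 h (3.7% to 4.3%) | 0.3% to 0.4% | at most × 1.010 |
| 24 h, 48 h measurable (13.3% to 16.5%) | 1.1% to 1.3% | at most × 1.13 |

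The expected half-width on the log scale is t(0.95, 10) × √ln(1 + 0.06²) × √(2/12) = 1.812 × 0.0599 × 0.408 = 0.044. At a ratio of 0.97 the expected 90% CI is therefore about 0.93 to 1.01. In the worst upward case, 0.97 × 1.013 with half-width 0.044 × 1.13 gives about 0.93 to 1.03. The worst downward case, 0.97/1.0105 with half-width 0.044 × 1.09, gives about 0.91 to 1.01. All lie well within 0.80 to 1.25.

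**The case against.** The best defence is that 10.3 is a specific rule for one situation and so overrides the general rule. It may also be loose wording for joining the neighbouring samples without imputing a value. Either reading is possible, but the SAP states neither. Even as a deliberate exception, 10.3 replaces a rule that is nearly exact here with one that biases AUC upward.

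The omission from SAP 1.2 is a thin point. Protocol 15.9 asks only that changes be described in the SAP, and 10.3 does describe one. That makes it a documentation gap, not a breach.

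The objections to the size of the effect do stand:

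- **The 24 h case is unlikely.** It needs a quantifiable 48 h value of about 0.019 to 0.028 ng/mL. A rough last measurable concentration implied by earlier studies, (AUC0-∞ − AUC0-t) × ln 2/T½, is much higher: (173 − 166) × 0.1510 = 1.06 and (168 − 160) × 0.1453 = 1.16 ng/mL in Table 3, and (73.63 − 59.80) × 0.1695 = 2.34 ng/mL in Table 1. Sampling in those studies may simply have stopped earlier. The LLOQ here is not given; the "limits of quantification range, will be provided in a Bioanalytical Phase Plan".
- **The 16 h and the 14 h plus 16 h cases need a measurable 24 h sample** (predicted 0.72 fasted, 0.93 fed ng/mL). If 24 h is BLQ, AUC0-t ends before the gap and the two rules agree. The largest single-sample excess is then about 1.7%, at 8 h.
- **The fed model peaks at 16.4 ng/mL**, against 22.3 in Table 3. Late-gap results depend mainly on half-life and gap length, so this limits precision, not direction.
- **The rule matters only if samples are missing**, in confined subjects with tightly timed draws.

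**Conclusion.** The inconsistency is real and the direction of the bias on the declining limb is a mathematical fact. The size is small: 0.2% to 2.1% of one profile's AUC0-∞ for a single gap between 6 and 16 h, and 3.7% to 4.3% if 14 h and 16 h are both missing. The 13% to 17% case arises only when 24 h is missing and 48 h is quantifiable. These percentages rest on the assumed one-compartment profiles and on an LLOQ low enough for the sample after the gap to be measurable. The trial-level figures assume one affected profile and a 6% CV. The AUC conclusion is unlikely to change. Cmax and the sample size are unaffected. This is a minor reconciliation, worth making because it removes an undeclared choice of method on a primary endpoint.

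**What to change.** Replace the last paragraph of SAP 10.3 with a sentence to this effect:

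> A missing sample is left out, and the area between the adjacent available samples is obtained by the linear-up/log-down rule of Section 11.4.2; AUC0-t stops at the last measurable concentration.

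If the linear rule is intended, keep it, but give the reason, list it in SAP 1.2 and cross-refer to it from SAP 11.4.2 so that the PK analyst applies it.

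Either option costs one or two sentences before database lock. No new data and no design change are needed.
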